## 5.4. Adverse Events

### Possible Risks (Potential Risks)

- Serious infections (defined as infections that are life-threatening, requiring intravenous (IV) antibiotics or hospitalization)
- Helminth parasitic infections
- Hypersensitivity/allergic reactions
- Immune complex disease (type III hypersensitivity reactions)
- Malignancies

### Adverse Events (Observed)

In the recent Phase 3 SIROCCO study [3], the most common (observed in > 3% of the patients) adverse events (AEs) were asthma, nasopharyngitis, upper respiratory tract infection, headache, bronchitis, sinusitis, influenza, acute sinusitis, back pain, cough, hypertension, pyrexia, nausea, rhinitis, pharyngitis, arthralgia, rhinitis allergic, viral infection, pain in extremity, dyspnea, gastro esophageal reflux disease, asthenia, dizziness and gastroenteritis.

In the recent Phase 3 CALIMA study [9], the most common (observed in > 3% of the patients) AEs were nasopharyngitis, asthma, upper respiratory tract infection, bronchitis, headache, sinusitis, hypertension, influenza, rhinitis, rhinitis allergic, nasal congestion, diarrhea, arthralgia, back pain, gastroenteritis, contusion, cough, pharyngitis, pyrexia, oropharyngeal pain, oral candidiasis, pneumonia bacterial and viral upper respiratory tract infection.

In both studies, the AEs showed a largely similar distribution between treatment and placebo arms.

## 5.5. Risk-benefit and Ethical Assessment

Benralizumab is primarily being studied in severe asthma where there are few treatment options for patients whose asthma remains uncontrolled on high dose ICS/LABA and oral corticosteroids [10]. In adult patients whose asthma was poorly controlled on medium-to-high dose ICS/LABA therapy, benralizumab at doses of  $\geq 20$  mg produced improvements in multiple metrics of asthma control including the annual rate of asthma exacerbations, lung function, ACQ-6 scores, and symptoms [6]. These findings have subsequently been confirmed in 2 large Phase 3 studies [3, 9] where a fixed dose of 30 mg was given either Q4W or Q8W.

Development of anti-drug antibodies (ADA) to benralizumab has been documented. Theoretical risks of developing ADA include decreased drug efficacy and hypersensitivity reactions (e.g., anaphylaxis or immune complex disease). Eosinophils are a prominent feature of the inflammatory response to helminthic parasitic infections and the presence of infiltrating eosinophils has been circumstantially associated with a positive prognosis in certain solid tumors. Therefore, there is a theoretical risk that prolonged eosinophil depletion may diminish the ability to defend against helminthic parasites, or negatively impact the natural history of certain malignant tumors. Risk minimization measures herein include exclusion of subjects with untreated parasitic infection and active or recent malignancy, in conjunction with the performance of routine pharmacovigilance activities.

The efficacy and safety data obtained to date support the continued clinical development of benralizumab in patients with asthma.

A detailed assessment of the overall risk/benefit of benralizumab is provided in the Investigator's Brochure.

## **6. STUDY OBJECTIVES**

### **6.1. Primary Objective**

- To compare the PK exposure following single SC administration of benralizumab by using APFS or AI devices

### **6.2. Secondary Objectives**

- To evaluate the PK of benralizumab administered to various anatomical injection sites and in subjects with different body weight ranges
- To evaluate the safety and tolerability of benralizumab
- To evaluate the immunogenicity of benralizumab

Refer to [Section 11.9.1](#) for PK parameters, [Section 9.3](#) for safety variables and [Section 9.4](#) for immunogenicity assessments.

## 7. OVERALL DESIGN AND PLAN OF THE STUDY

### 7.1. Overall Study Design

This study will be a multicenter, randomized, open-label, parallel group Phase 1 study designed to compare benralizumab PK exposure in healthy subjects following single SC administration of fixed 30 mg dose of benralizumab by using APFS and single-use AI. Eligible subjects will be healthy subjects aged 18 to 55 years, with a body weight of 55 to 100 kg and a body mass index (BMI) of 18 to 29.9 kg/m^2. A total of 180 subjects will be randomized. Randomization will be stratified by weight group (55 to 69.9 kg, 70 to 84.9 kg and 85 to 100 kg), and within each of the 3 weight groups, subjects will be randomized 1:1:1:1:1:1 to 1 of the 6 combinations of treatment (APFS or AI) with injection site (upper arm, abdomen or thigh), presented in [Table 1](#). This study will be performed at 2 study centers.

**Table 1 Design of a Pharmacokinetic Comparability Study in Healthy Subjects for Benralizumab Accessorized Pre-Filled Syringe and Autoinjector Devices**

Number of Subjects		APFS			AI			Total
		Upper Arm	Abdomen	Thigh	Upper Arm	Abdomen	Thigh	
Body Weight	55.0 to 69.9 kg	10	10	10	10	10	10	60
	70.0 to 84.9 kg	10	10	10	10	10	10	60
	85.0 to 100.0 kg	10	10	10	10	10	10	60
Total		90			90			180

AI: Autoinjector; APFS: Accessorized pre-filled syringe device

The study will comprise of:

- A screening period of maximum of 28 days,
- One treatment period during which subjects will be resident from the day before dosing (Day -1) until 2 hours after dosing on Day 1. The subjects will then return to the center for ambulant visits on Days 2, 4, 5, 6, 8, 15, 29 and 43, and
- An End-of-Treatment visit on Day 57 (Week 8).

After a screening period of up to 28 days, eligible subjects will be admitted to the unit on Day -1 (1 day before dosing) to reassess their eligibility. Subjects who meet eligibility criteria will be randomized on Day 1 to receive a single dose of 30 mg benralizumab by either APFS or AI device. The study will be completed after the End-of-treatment visit on Day 57 (Week 8).

#### 7.1.1. End of Study

The end of study is defined as the last subject's last visit to the clinical unit.

### 7.1.2. Interim Analyses

No interim analyses will be performed in this study.

### 7.1.3. Expected Duration of the Study

Each subject will be involved in the study for 12 to 13 weeks (8 to 9 weeks active participation) and 28 days screening period.

## 7.2. Schedule of Assessments

The schedule of assessments displaying assessments/tasks and time points is presented in [Table 2](#).

**Table 2** Schedule of Assessments

	Screening Day -28 to -2	Day -1	Days 1 to 57
Informed consent	X		
Inclusion/exclusion criteria	X	X	
Height	X		
Weight	X	X	
Other demographic data	X		
Medical history	X		
Urinary drug and alcohol screen	X	X	
Serum pregnancy and FSH test	X		
Urine pregnancy test (dipstick)		X	Day 57
Serology	X		
Randomization			Day 1
Study residency:			
Check-in		X	
Check-out			Day 1 (2 h post-dose)
Non-residential visit	X		Days 2, 4, 5, 6, 8, 15, 29, 43 and 57
IMP (Benralizumab) administration:			Day 1 (0 h)
Safety and tolerability:			
Adverse event questioning			Pre-dose and 2 h post-dose (Day 1), Days 2, 4, 5, 6, 8, 15, 29, 43 and 57
Vital signs	X	X	Pre-dose and 2 h post-dose (Day 1), Days 2, 4, 5, 6, 8, 15, 29, 43 and 57
12-lead electrocardiogram	X		Days 1, 29 and 57
Clinical laboratory evaluations	X	X	Days 8, 29 and 57
Physical examination	X	X(brief)	Days 8, 29 and 57 (2 h post dose (brief))
Pharmacokinetics			
Serum benralizumab concentration a			Pre-dose (Day 1), Days 2, 4, 5, 6, 8, 15, 29, 43 and 57
Immunogenicity			
ADA			Pre-dose (Day 1), Days 29 and 57

ADA: anti-drug antibody; FSH: follicle-stimulating hormone; IMP: investigational medicinal product

a Samples to determine serum Benralizumab concentrations will be collected at consistent times across the different study days.

### 7.3. Order of Assessments

It is important that PK sampling occurs as close as possible to the scheduled time. In order to achieve this, other assessments scheduled at the same time may be initiated prior to the time point.

The sequence at a particular time point is:

1. Electrocardiograms (ECGs), if applicable
2. Vital signs (systolic and diastolic blood pressure [BP], pulse rate and oral temperature)
3. Pharmacokinetic blood sampling (will be drawn at the specified time points)
4. Anti-drug antibody and safety laboratory blood sampling.

### 7.4. Restrictions During the Study

The following restrictions apply for the specified times during the study period:

1. On Day 1 of the treatment period, subjects will be fasted (except for water) for 10 hours prior to dosing until 2 hours after dosing. Subjects will receive a meal before they are discharged from the clinical unit.
2. Subjects should abstain from alcohol for 72 hours prior to check-in on Day -1, until after their Day 15 PK sampling visit.
3. Subjects should abstain from caffeine-containing foods and beverages for 24 hour prior to check-in on Day -1, until discharge from the clinical unit.
4. During admission period, subjects will receive a standard diet, which excludes alcohol-containing products. No additional food or beverages must be consumed while in the clinical unit.
5. During the subjects' outpatient periods, subjects should abstain from consuming high-energy drinks (e.g., red bull), food containing poppy seeds and any over-the-counter (OTC) medication or herbal preparations until after their End-of-Treatment Visit has been completed. Subjects should also limit their caffeine intake to equivalent of 3 cups of coffee per day (1 cup = 250 mL soda, 180 mL coffee or 240 mL tea). Subjects should consume no more than 2 units of alcohol per day (1 unit = 10 mL or 8 g of pure alcohol) and completely abstain from 72 hours prior next visit.
6. Subjects will be required to abstain from blood or plasma donation until 3 months after the final medical examination at the study End-of-Treatment visit.
7. Medication restrictions. Refer to [Section 8.7](#).

## **7.4.1. Reproductive Restrictions**

### **7.4.1.1. *Women of Non-Child-Bearing Potential***

Women of non-child-bearing potential are defined as female subjects who are permanently surgically sterilized or post-menopausal.

Permanent sterilization includes hysterectomy and/or bilateral oophorectomy and/or bilateral salpingectomy but excludes bilateral tubal ligation.

Females are considered post-menopausal if they have had amenorrhea for at least 12 months or more following cessation of all exogenous hormonal treatments and follicle-stimulating hormone (FSH) levels are in the post-menopausal range.

### **Pregnancy Testing**

Women of non-child-bearing potential can be included only after a negative highly sensitive serum pregnancy test. Additionally urine pregnancy testing will be done as per the schedule of assessments.

### **7.4.1.2. *Male Subjects***

#### **Restrictions for Male Subjects**

There is no information about effects that benralizumab could have on the development of the fetus in humans. Therefore, it is important that women of child-bearing potential, who are the partners of male subjects, do not become pregnant during the study and for a total period of 16 weeks after the male subject has attended the study End-of-Treatment visit.

As a precaution, all male subjects should avoid fathering a child by either true abstinence\* or use together, with their female partner/spouse, a highly effective contraception form of birth control in combination with a barrier method, starting from the time of investigational medicinal product (IMP) administration until 16 weeks after the study End-of-Treatment visit.

\* True abstinence: When this is in line with the preferred and usual lifestyle of the subject. (Periodic abstinence [e.g., calendar, ovulation, symptothermal, post-ovulation methods], declaration of abstinence for the duration of a trial and withdrawal are not acceptable methods of contraception).

Highly effective contraception is defined as having a low failure rate, i.e., less than 1% per year when used consistently and correctly. Highly effective contraception forms of birth control include:

- Hormonal contraception, i.e., oral, injectable or implantable hormonal contraceptives for the female partner/spouse (Note: Not all oral contraception methods have a low failure rate.);
- Hormonal or non-hormonal intrauterine device, established intrauterine device (IUD, loop) or intrauterine system for the female partner/spouse;
- The subject has undergone effective surgical sterilization before he entered the clinical study;
- The subject's female partner/spouse that has undergone effective surgical sterilization before the subject entered the clinical study and she is the sole sexual partner of the subject during the clinical study.

Barrier methods of contraception include:

- Condom (without spermicidal foam/gel/film/cream/suppository or fat- or oil-containing lubricants);
- Occlusive cap (diaphragm or cervical/vault caps) with spermicidal foam/gel/film/cream/suppository for the female partner/spouse

Male subjects who have been sterilized are required to use one barrier method of contraception (condom) from the time of IMP administration until after the End-of-Treatment visit.

### **Sperm Donation**

Male subjects should not donate sperm for the duration of the study and for at least 16 weeks after the study End-of-Treatment visit.

### **Pregnancy**

Subjects will be instructed that if their partner becomes pregnant during the study this should be reported to the Investigator. The Investigator should also be notified of pregnancy occurring during the study but confirmed after completion of the study. In the event that a subject's partner is subsequently found to be pregnant after the subject is included in the study, then consent will be sought from the partner and if granted any pregnancy will be followed and the status of mother and/or child will be reported to the Sponsor after delivery.

A pregnancy notification form and follow-up will be completed.

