## Study Design

This study will be a multicenter, randomized, open-label, parallel group Phase 1 study designed to compare benralizumab PK exposure in healthy subjects following single SC administration of fixed 30 mg dose of benralizumab by using APFS and single-use AI. Eligible subjects will be healthy subjects aged 18 to 55 years, with a body weight of 55 to 100 kg and a body mass index of 18 to 29.9 kg/m^2. A total of 180 subjects will be randomized. Randomization will be stratified by weight group (55 to 69.9 kg, 70 to 84.9 kg and 85 to 100 kg), and within each of the 3 weight groups, subjects will be randomized 1:1:1:1:1 to 1 of the 6 combinations of treatment (APFS or AI) with injection site (upper arm, abdomen or thigh), presented in Table 1. This study will be performed at 2 study centers.

**Table 1 Design of a Pharmacokinetic Comparability Study in Healthy Subjects for Benralizumab Accessorized Pre-Filled Syringe and Autoinjector Devices**

Number of Subjects		APFS			AI			Total
		Upper Arm	Abdomen	Thigh	Upper Arm	Abdomen	Thigh	
Body Weight	55.0 to 69.9 kg	10	10	10	10	10	10	60
	70.0 to 84.9 kg	10	10	10	10	10	10	60
	85.0 to 100.0 kg	10	10	10	10	10	10	60
Total		90			90			180

AI: Autoinjector; APFS: Accessorized pre-filled syringe device

The study will comprise of:

- A screening period of maximum of 28 days,
- One treatment period during which subjects will be resident from the day before dosing (Day -1), until 2 hours after dosing on Day 1. The subjects will then return to the center for ambulant visits on Days 2, 4, 5, 6, 8, 15, 29 and 43, and
- An End-of-Treatment visit on Day 57 (Week 8).

After a screening period of up to 28 days, eligible subjects will be admitted to the unit on Day -1 (1 day before dosing) to reassess their eligibility. Subjects who meet eligibility criteria will be randomized on Day 1 to receive a single dose of 30 mg benralizumab by either APFS or AI device. The study will be completed after the End-of-Treatment visit on Day 57 (Week 8).

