### **7.5.1. Inclusion Criteria**

For inclusion in the study, subjects should fulfill the following criteria:

1. Provision of signed and dated, written informed consent prior to any study specific procedures.
2. Healthy male and/or female subjects of non-child-bearing potential aged 18 to 55 years (inclusive) with suitable veins for cannulation or repeated venipuncture.
3. Females must have a negative pregnancy test at screening and on admission to the unit, must not be lactating and must be of non-child-bearing potential, confirmed at screening by fulfilling one of the following criteria:
  - 3.1. Post-menopausal defined as amenorrhea for at least 12 months or more following cessation of all exogenous hormonal treatments and FSH levels in the post-menopausal range.
  - 3.2. Documentation of irreversible surgical sterilization by hysterectomy, bilateral oophorectomy or bilateral salpingectomy but not tubal ligation.
4. All male subjects who are sexually active must agree to use a highly effective contraception form of birth control in combination with a barrier method from the first dose of IMP until 16 weeks after the study End-of-Treatment visit.
5. Have a BMI between 18 and 29.9 kg/m^2 inclusive and weigh at least 55 kg and no more than 100 kg inclusive.
6. Only applicable to the PAREXEL Early Phase Clinical Unit Berlin: Able to understand, read and speak the German language.

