## **12.2. Recording of Adverse Events**

### **12.2.1. Time Period for Collection of Adverse Events**

Adverse Events will be collected from randomization throughout the treatment period up to and including the End-of-Treatment visit.

SAEs will be recorded from the time of informed consent.

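### The protocol's instruction to report a partner pregnancy stops with the study, although its own fetal-risk period runs 16 weeks past the End-of-Treatment visit

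*Protocol*

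**What the plan says.** Protocol Section 7.4.1.2 (Male Subjects) sets several periods.

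- **Restrictions for Male Subjects.** Because fetal effects in humans are unknown, partners should be women who "do not become pregnant during the study and for a total period of 16 weeks after" the subject's End-of-Treatment visit. Contraception runs from dosing to the same end point.
- **Sperm Donation.** Male subjects "should not donate sperm for the duration of the study and for at least 16 weeks" after that visit.
- **Inclusion criterion 4 (Section 7.5.1).** Sexually active men agree to contraception "from the first dose of IMP until 16 weeks after the study End-of-Treatment visit".
- **Pregnancy, first sentence.** "Subjects will be instructed that if their partner becomes pregnant during the study this should be reported to the Investigator".
- **Pregnancy, second sentence.** "The Investigator should also be notified of pregnancy occurring during the study but confirmed after completion of the study".
- **Pregnancy, third sentence.** This opens "In the event that a subject's partner is subsequently found to be pregnant after the subject is included in the study". It goes on to provide for the partner's consent, follow-up of the pregnancy and a report to the Sponsor after delivery. It has no end date.

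Three other places bear on what counts as the study and on what happens afterwards. The Synopsis (Study Design) and Section 7.1 say the study is completed after the Day 57 visit. Section 7.1.1 defines the end of study as the last subject's last visit. Section 12.2.1 says: "Adverse Events will be collected from randomization throughout the treatment period up to and including the End-of-Treatment visit". The schedule in Section 7.2 (Table 2) has no contact after Day 57.

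**The concern.** The protocol treats the 16 weeks after the End-of-Treatment visit as a period of possible fetal risk and restricts male subjects accordingly. The instruction that would bring a pregnancy to the site's attention does not cover that period. The second sentence allows for late confirmation, but the pregnancy must still have occurred while the study was running. A later conception is outside both sentences.

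Follow-up of partner pregnancies is how this plan would learn about a risk that it calls unknown. A pregnancy the site never hears about cannot be followed, even though the third sentence would provide for it. The point is one of safety reporting and does not touch the AUC and Cmax comparison.

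**Working it through.** The plan gives no figure of its own here. The check compares the windows and then sizes the gap.

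**Does the study include the 16 weeks?** The restriction on partners and the sperm-donation rule each name the study and then add the 16 weeks. If the study already included them, the addition would be redundant. The notification sentences name only the study.

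**Protected period.** Dosing is on Day 1 and the End-of-Treatment visit on Day 57. 16 weeks = 16 × 7 = 112 days, and 57 + 112 = Day 169. Day 1 to Day 169 is 168 days, or 24 weeks.

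**Reading A: the study ends for each subject at Day 57** (Synopsis; Section 7.1). Uncovered: 112/168 = 66.7%, for every male subject.

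**Reading B: the study ends at the last subject's last visit** (Section 7.1.1). The Synopsis (Study Period) plans first consent in November 2016 and last completion in June 2017. Assumptions: up to 28 days of screening, and even enrolment.

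- First dose: 1 November to 28 December 2016.
- Last visit: 1 to 30 June 2017. Last dose is 56 days earlier: 6 April to 5 May 2017.
- Span S from first to last dose: 99 days (28 December to 6 April) to 185 days (1 November to 5 May).
- A subject dosed t days before the last subject has max(0, 112 − t) uncovered days.

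| Subject | S = 99 days | S = 185 days |
|---|---|---|
| First | 112 − 99 = 13 days (7.7%) | 0 days |
| Last | 112 days (66.7%) | 112 days (66.7%) |
| Mean | 112 − 99/2 = 62.5 days (37.2%) | (112²/2)/185 = 33.9 days (20.2%) |

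**Expected conceptions in the uncovered time.** Section 7.4.1.2 defines highly effective contraception as failing in less than 1% per year. As a ceiling, take all 180 subjects to be men with partners able to conceive.

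- Reading A: 180 × 0.01 × 16/52 = 0.55.
- Reading B: 180 × 0.01 × 33.9/365.25 = 0.17, to 180 × 0.01 × 62.5/365.25 = 0.31.
- Reading A with an assumed 5% per year under imperfect use (not a figure from the documents): 180 × 0.05 × 16/52 = 2.8.

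**The case against.** The strongest reply is that the third sentence already covers a late pregnancy. It has no end date, and a site reading the whole paragraph might well ask subjects to report any partner pregnancy after inclusion. That stands as far as follow-up goes. But the sentence says what happens once a pregnancy is found. It does not tell the subject to report one, and after Day 57 the plan states no contact at which the site would find out.

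Four further points deserve an answer.

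- **Formal definition of the end of study.** Section 7.1.1 favours reading B, which narrows the gap, nearly or wholly closing it for the first subject. It leaves the last subject where reading A does, and makes the duty depend on enrolment order.
- **SAE rules.** Section 12.1.2 counts a birth defect as serious, and Section 12.2.1 gives no end date for recording SAEs. So the outcome is not wholly outside the safety text. Neither section asks a subject to report a partner's conception.
- **Consent form.** What subjects are actually told may be set out there, and those pages were not available. A longer instruction there cannot be ruled out. The point therefore concerns the protocol text.
- **Size.** The 67% is a share of days, not of risk, and 0.55 is an upper bound at the stated failure rate. Women of non-child-bearing potential may enrol, sterilization is an accepted method, and a barrier is required as well. This is correct and limits the weight of the point.

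**Conclusion.** The concern holds. The notification window in the protocol is shorter than the risk period the protocol sets for itself. The uncovered share is 67% of the 168 protected days if the study ends for each subject at Day 57, which is the more natural reading because the 16 weeks are named separately from the study. With the trial-level end of study, the mean is 20% to 37% under the planned dates and even enrolment.

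The expected number of affected pregnancies is small: below about 0.55 on the first reading and 0.17 to 0.31 on the second, all at the 1% per year ceiling with every subject counted as a man with a fertile partner. The change is worth making because it is cheap and because, with so few events, each one missed is a real loss of information. It is a recommended correction to safety reporting, without bearing on the primary analysis.

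**What to change.** In the first two sentences of the Pregnancy paragraph (Section 7.4.1.2), replace the limit to the study with a window running from dosing to 16 weeks past the subject's End-of-Treatment visit. Keep the allowance for later confirmation, so that a conception inside the window is reported even if it is confirmed after the window closes. Leave the third sentence as it is. At the Day 57 visit, repeat the instruction and give a site contact. Use the existing pregnancy notification form.

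The cost is one phrase in two sentences and a short reminder at a visit already scheduled. If the consent form has the same limit it needs matching wording, and Section 3.6 then calls for ethics committee approval before the revised form is used. Sites would accept occasional subject-initiated reports for 16 weeks after the last visit, probably none or one across the trial if contraception is used as required. No visit, sample or analysis is added.
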